5.5 General Concomitant Medication and Supportive Care Guidelines

Any medication taken by a subject during the course of the study and the reason for its use will be documented in the clinical source documentation.

5.5.1 Supportive Care Guidelines

Subjects should receive appropriate supportive care measures as deemed necessary by the treating investigator. Suggested supportive care measures for the management of adverse events with potential immunologic etiology are outlined below. Where appropriate, these guidelines include the use of oral or intravenous treatment with corticosteroids as well as additional anti-inflammatory agents if symptoms do not improve with administration of corticosteroids. Note that several courses of steroid tapering may be necessary as symptoms may worsen when the steroid dose is decreased. For each disorder, attempts should be made to rule out other causes such as metastatic disease or bacterial or viral infection, which might require additional supportive care. The treatment guidelines are intended if the events are suspected as related to nivolumab or ipilimumab.

It may be necessary to perform conditional procedures such as bronchoscopy, endoscopy, or skin photography as part of evaluation of the event. If after the evaluation, the event is deemed unrelated to immunotherapy, the investigator does not need to follow the treatment guidance (as outlined below). Refer to Section 6 for dose modification.

Pneumonitis:

- For Grade 2 events, treat with systemic corticosteroids.
- For **Grade 3-4 events**, immediately treat with intravenous steroids. Administer additional anti-inflammatory measures, as needed.
- When symptoms improve to Grade 1 or less, taper steroid over 4 or more weeks.
- Add prophylactic antibiotics for opportunistic infections in the case of prolonged steroid administration.

Infusion Reactions:

• Signs and symptoms usually develop during or shortly after drug infusion and generally resolve completely within 24 hours of completion of infusion.

Diarrhea/Colitis:

Carefully monitor for signs and symptoms of enterocolitis (e.g. diarrhea, abdominal pain, blood or mucus in stool, with or without fever) and of bowel perforation (e.g. peritoneal signs and ileus).

- Advised all to drink liberal quantities of clear fluids. If oral fluid intake is insufficient, IV fluid and electrolytes supplementation is advised. For Grade 2 or higher diarrhea, consider GI consultation and endoscopy to confirm or rule out colitis.
- For Grade 2 events, administer oral corticosteroids.
- For Grade 3 or 4 events, treat with IV followed by high dose oral steroids.

When symptoms improve to Grade 1 or less, taper steroid over 4 or more weeks.

Hypophysitis:

- For **Grade 2** events, treat with corticosteroids.
- For Grade 3-4, treat initially with IV followed by oral corticosteroids.
- When symptoms improve to Grade 1 or less, taper steroid over 4 or more weeks.
- Replace hormones as warranted as the steroid dose is tapered

Type 1 diabetes mellitus [*if new onset, Grade* \geq *3 Hyperglycemia, associated with ketosis (ketonuria) or metabolic acidosis (DKA)*]

- Insulin replacement therapy is recommended for Type I diabetes mellitus and for Grade 3-4 hyperglycemia associated with metabolic acidosis or ketonuria.
- Evaluate serum glucose, metabolic panel, glycosylated hemoglobin, and C-peptide as well as urine ketones.

Hyperthyroidism or Hypothyroidism:

Thyroid disorders can occur at any time during treatment. Monitor patients for changes in thyroid function (at the start of treatment, periodically during treatment, and as indicated based on clinical evaluation) and for clinical signs and symptoms of thyroid disorders.

- Grade 2 hyperthyroidism events (and Grade 2-4 hypothyroidism):
 - In hyperthyroidism, non-selective beta-blockers (e.g. propranolol) preferred.
 - In hypothyroidism, thyroid hormone replacement therapy with levothyroxine or liothyroinine as per standard of care.
- **Grade 3-4** hyperthyroidism
 - Treat initially with IV followed by oral corticosteroids. When symptoms improve to Grade 1 or less, taper steroid over 4 or more weeks.
 - Replace hormones as warranted as the steroid dose is tapered

Hepatic:

- For **Grade 2** events, monitor liver function tests more frequently (consider weekly) until returned to baseline. Treat with IV or oral corticosteroids
- For Grade 3-4 events, treat with intravenous corticosteroids for 24-48 hours.
- When symptoms improve to Grade 1 or less, taper steroid over 4 or more weeks.

Immune-mediated myocarditis

- For suspected immune-mediated myocarditis, ensure adequate evaluation to exclude other etiologies, and administer corticosteroids as appropriate.
- Permanently discontinue the related immunotherapy for confirmed immune-mediated myocarditis.

Renal Failure or Nephritis:

- For Grade 2 events, treat with oral corticosteroids.
- For Grade 3-4 events, treat with IV or oral corticosteroids.
- When symptoms improve to Grade 1 or less, taper steroid over 4 or more weeks.

Stevens-Johnson syndrome (SJS) and toxic epidermal necrolysis (TEN)

- For signs or symptoms of SJS or TEN, withhold immunotherapy and refer the patient for specialized care for assessment and treatment.
- If SJS or TEN is confirmed, permanently discontinue the related immunotherapy.

Refer to Appendices E and F for Toxicity Management Algorithms for Nivolumab and Ipilimumab, respectively.

TREATMENT GUIDELINES FOR INFUSION REACTIONS				
NCI CTCAE Grade	Treatment	Premedication for Next Dose		
Grade 1 Mild reaction; infusion interruption and intervention not indicated	Increase monitoring of vital signs as medically indicated until medically stable in the opinion of the investigator.	None		
Grade 2 Requires infusion interruption but responds promptly to symptomatic treatment (e.g., antihistamines, NSAIDS, narcotics, IV fluids); prophylactic medications indicated for ≤24 hours	 Stop Infusion and monitor Additional therapy options: IV fluids Antihistamines NSAIDS Acetaminophen Narcotics Increase monitoring of vital signs as medically indicated until medically stable in the opinion of the investigator. If symptoms resolve within 1 hour of stopping infusion, the infusion may be restarted at 50% of the original rate (e.g., from 100 mL/hr to 50 mL/hr). Otherwise dosing held until symptoms resolve and premedication required for the next scheduled dose. 	 Subject may be premedicated 1.5h (± 30 minutes) prior to infusion with: Diphenhydramine 50 mg PO (or equivalent dose of antihistamine) Acetaminophen 500-1000 mg PO (or equivalent antipyretic 		
	Subjects who develop Grade 2 toxicity despite adequate premedication should discontinue therapy.			
Grades 3 or 4 Grade 3: Prolonged (i.e., not rapidly responsive to medication and/or brief interruption); recurrence of symptoms following initial improvement; hospitalization indicated for other sequelae (e.g., renal impairment, pulmonary infiltrates) Grade 4: Life-threatening; pressor or ventilatory support indicated	 Stop Infusion. Additional medical options: IV fluids Antihistamines NSAIDS Acetaminophen Narcotics Oxygen Pressors Corticosteroids Epinephrine Increase monitoring of vital signs as medically indicated until medically stable in the opinion of the investigator. Hospitalization may be indicated. Permanently discontinue related immunotherapy 	No subsequent dosing		
Appropriate resuscitation equipment should be available in the room and a physician readily available during the period of drug administration.				

5.5.2 Diet/Activity/Other Considerations

Subjects should maintain a normal diet unless modifications are required to manage an AE such as diarrhea, nausea or vomiting.

5.6 Contraception

Nivolumab and ipilimumab have adverse effects on a fetus in utero and may have transient adverse effects on the composition of sperm.

Male subjects are considered to be of non-reproductive potential if they have azoospermia (whether due to having had a vasectomy or due to an underlying condition).

Female subjects are considered of non-reproductive potential if any below apply:

- 1. Congenital or acquired condition that prevents childbearing
- 2. Postmenopausal (12 or more months with no menses without an alternative medical cause; in women < 45 years of age a high follicle stimulating hormone (FSH) level in the postmenopausal range may be used to confirm a post-menopausal state in women not using hormonal contraception or hormonal replacement therapy. In the absence of 12 months of amenorrhea, a single FSH measurement is insufficient.
- 3. Status post hysterectomy and/or bilateral oophorectomy, bilateral salpingectomy or bilateral tubal ligation/occlusion, 6 or more weeks prior to start of treatment.

Female and male subjects of reproductive potential must agree to avoid becoming pregnant or impregnating a partner, respectively, while receiving study drug and for 5 months for female and 7 months for male subjects after the last dose of study drug by any of the following methods:

- Abstinence from heterosexual activity
 ** Abstinence (relative to heterosexual activity) can be used as the sole method of
 contraception if it is consistently employed as the subject's preferred and usual lifestyle and if
 considered acceptable by local regulatory agencies and ERCs/IRBs. Periodic abstinence
 (e.g., calendar, ovulation, sympto-thermal, post-ovulation methods, etc.) and withdrawal are
 not acceptable methods of contraception.
- 2. Acceptable contraception during heterosexual activity by subject or partner
 - Single method (one of the following is acceptable):
 - intrauterine device (IUD)
 - vasectomy of a female subject's male partner
 - contraceptive rod implanted into the skin
 - Combination method (requires use of two of the following):
 - diaphragm with spermicide (NOT in conjunction with cervical cap/spermicide)
 - cervical cap with spermicide (nulliparous women only)
 - contraceptive sponge (nulliparous women only)
 - male condom or female condom (cannot be used together)
 - hormonal contraceptive: oral contraceptive pill (estrogen/progestin pill or progestinonly pill), contraceptive skin patch, vaginal contraceptive ring, or subcutaneous contraceptive injection

** If a contraceptive method listed above is restricted by local regulations/guidelines, then it does not qualify as an acceptable method of contraception for subjects participating at sites in this country/region.

In order to participate in the study subjects of childbearing potential must adhere to the contraception requirement (described above) from the day of study medication initiation (or 14 days prior to the initiation of study medication for oral contraception) throughout the study period up to 5 months for female and 7 months for male subjects after the last dose of trial therapy. If there is any question that a subject of childbearing potential will not reliably comply with the requirements for contraception, that subject should not be entered into the study. Subjects should be informed that taking the study medication might involve unknown risks to the fetus (unborn baby) if pregnancy were to occur during the study.

5.6.1 **Pregnancy**

If a subject inadvertently becomes pregnant while on treatment, the subject will immediately be removed from the study. The site will contact the subject at least monthly and document the subject's status until the pregnancy has been completed or terminated. The outcome of the pregnancy will be reported to BMS within 2 working days if the outcome is a serious adverse experience (e.g., death, abortion, congenital anomaly, or other disabling or life-threatening complication to the mother or newborn).

The study investigator will make every effort to obtain permission to follow the outcome of the pregnancy and report the condition of the fetus or newborn. If a male subject impregnates his female partner the study personnel at the site must be informed immediately and the pregnancy reported to BMS.

5.6.2 Nursing Women

It is unknown whether nivolumab or ipilimumab are excreted in human milk. Since many drugs are excreted in human milk, and because of the potential for serious adverse reactions in the nursing infant, subjects who are breast-feeding are not eligible for enrollment.

5.7 Subject Withdrawal/Discontinuation Criteria

Subjects may withdraw consent at any time for any reason or withdrawn from the trial at the discretion of the investigator for any untoward effect. A subject may also be withdrawn by the investigator or the Sponsor if enrollment is inappropriate, the trial plan is violated, or for administrative and/or other safety reasons.

5.8 Criteria for Taking a Participant off Protocol Therapy

Duration of therapy will depend on individual response, evidence of disease progression and tolerance. Treatment will be discontinued for clinical or radiographic progression of disease, intolerance despite dose modification (defined as NCI Common Terminology Criteria for Adverse Events (CTCAE) version 4.0 Grade 3 or 4 that does not return to Grade 1 or 2 after interruption or reduction of dose for 4 weeks), or patient withdrawal. A patient who experiences a dose-limiting toxicity (DLT) can remain on study at a reduced dose, if deemed by the physician to be safe and beneficial for the patient to continue.

In the absence of treatment delays due to adverse events, treatment may continue until one of the following criteria applies:

- Global deterioration of health-related symptoms (clinical progression),
- Confirmed radiographic disease progression,

- Intercurrent illness that prevents further administration of treatment,
- Unacceptable adverse event(s),
- Treatment interruption for more than 4 consecutive weeks due to intolerance despite appropriate dose modification,
- Participant decides to withdraw from the study, or
- General or specific changes in the participant's condition render the participant unacceptable for further treatment in the opinion of the treating investigator,
- Protocol non-compliance,
- Pregnancy,
- Lost to follow-up, or
- Study termination by Investigator, Institution or IRB.

If a patient does not return for a scheduled visit, every effort should be made to contact the patient. In any circumstance, every effort should be made to document patient outcome, if possible. The Investigator should inquire about the reason for withdrawal, request that all unused investigational product(s) be returned, request the patient to return for a final visit, if applicable, and advise follow-up with the patient regarding any unresolved adverse events.

If the patient withdraws from the trial and also withdraws consent for disclosure of future information, then no further evaluations should be performed and no additional data should be collected. The Investigator may retain and continue to use any data collected before such withdrawal of consent.

If the participant undergoes another surgery for presumed tumor progression but pathological findings are consistent with pseudoprogression (inflammation and necrosis rather than active tumor), the participant will deemed to not have had tumor progression and may continue treatment with nivolumab after review with the principal investigator.

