1. OBJECTIVES

1.1 Study Design

This is an open-label, phase II trial with two parallel arms, two-stage design and appropriate stopping rules for poor efficacy. Arm A will enroll patients without prior PD1/PDL1 checkpoint inhibitor, while Arm B will enroll patients with prior PD1/PDL1 checkpoint inhibitor. We expect to enroll at least 30 (15 in each Arm) and a maximum of 60 (30 in each Arm) evaluable subjects. All subjects will receive TTFields therapy plus nivolumab infusions for a maximum of 24 months, plus/minus concurrent ipilimumab for a maximum of 4 doses (see study schema below).

The NovoTTF200A (OptuneTM) device is worn continuously for \geq 75% of the time, ranging 18 hours/day uninterrupted to 22 hours/day with 2-3 days off monthly. TTFields therapy begins once approved by insurance and an in-home initiation arranged. The goal is to start within 1 month of trial enrollment. Treatment is planned for ~24 months.

Infusions will start within 1 week of study enrollment. Nivolumab will be dosed every 2 weeks IV 240 mg as monotherapy and 3 mg/kg with ipilimumab. Nivolumab therapy will not exceed 24 months. Ipilimumab starts with the second infusion of nivolumab for Arm B (prior PD1/PDL1 checkpoint inhibitor) or after progression on nivolumab monotherapy for Arm A (no prior PD1/PDL1 checkpoint inhibitor). Ipilimumab infusions will be dosed as 1 mg/kg once every 6 weeks for a maximum of 4 doses (24 weeks). Infusions will continue until a maximum of 24 months or when there is confirmed tumor progression, intolerable adverse effects or withdrawal of consent.

All patients will undergo clinical evaluation prior to each infusion every 2 weeks until the maximum 24 months of therapy, thereafter every 8 weeks during the maintenance phase. Neuroimaging studies (contrast-enhanced brain MRI or CT for patients unable to undergo MRI) and quality of life FACT-BR questionnaires will be administered at baseline then every 6 weeks during the treatment phase or every 8 weeks during the maintenance phase until off study.

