5. TREATMENT PLAN

5.1 Study Design

This is an open-label Phase II trial with two parallel arms, two-stage design with appropriate stopping rules for poor efficacy. Arm A will enroll patients without prior history of any PD1/PDL1 checkpoint inhibitor, while Arm B will enroll patients with prior PD1/PDL1 checkpoint inhibitor. We expect to enroll at least 30 (15 in each Arm) and a maximum of 60 (30 in each Arm) evaluable subjects on this study. The study schema is depicted below.

NovoTTF200A (Optune) is a device to be worn continuously for a goal of \geq 75% of the time, ranging from 18 hours daily nonstop or 22 hours daily with 2-3 days off monthly. Patients will be encouraged to meet compliance goals via timely feedback and troubleshooting concerns. TTFields therapy begins once approved by insurance and an in-home initiation visit scheduled. The goal is to start within 1 month of starting immunotherapy infusions. Treatment is planned for ~24 months.

Infusions will start within 14 days of sreening/baseline visits. Nivolumab will be dosed every 2 weeks IV 240 mg as monotherapy and 3 mg/kg with ipilimumab. Nivolumab will not exceed 48 doses (24 months). Ipilimumab starts with the second infusion of nivolumab for Arm B (prior immunotherapy) or after progression on single agent nivolumab for Arm A (no prior immunotherapy). Ipilimumab infusions will be dosed as 1 mg/kg once every 6 weeks for a maximum of 4 doses (24 weeks).

Infusions will continue until maximum duration of ipilimumab and nivolumab therapy or when there is confirmed tumor progression, death, intolerable adverse effects or withdrawal. After the maximum of 24 months of therapy, clinical, radiographic and quality of life assessments are performed every 8 weeks until or when there is confirmed tumor progression, death, or withdrawal. One treatment cycle is defined as 6 weeks for the initial 24 months, thereafter every 8 weeks will define observation cycles.

Reported adverse events and potential risks are described in Section 7. Dose modifications are described in Section 6. No investigational or commercial agents or therapies other than those described below may be administered with the intent to treat the participant's malignancy.

5.2 **Pre-Treatment Criteria**

All patients must sign an informed consent prior to any study-specific procedure. For screening, patients will have the following tests done at the treating institution or in a local lab within 14 days of treatment initiation:

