5.3 Treatment and Evaluation/ Observation Cycles

Blood draws are also performed within 2 days of each infusion. Screening/ Baseline lab results may be used for C1D1 if performed within 14 days of initial treatment. Hematology and blood chemistry panel results must be reviewed by an investigator prior to each infusion. After the maximum of 24 months of therapy, blood draws will only be performed with every clinical and radiographic assessment every 8 weeks.

Prior to each infusion every 2-3 weeks and beyond the initial 24 months every 8 weeks, patients will undergo physical examination, neurological exam, and KPS assessment. Response assessment by MRI or CT and FACT-BR quality of life questionnaires will be performed every 6 weeks for the initial 24 months of therapy and thereafter every 8 weeks. Targeted questioning will collect adverse events and concomitant medications.

To confirm objective response (OR), partial or complete response (see section 11.1 for definitions) by tumor measurements must be confirmed by repeat assessments performed ≥ 4 weeks after the criteria for response are first met. Progression should also be confirmed by repeat scans ≥ 4 weeks after progression first suspected on MRI or CT.

If the participant undergoes another surgery for presumed tumor progression, but pathological findings are consistent with pseudoprogression, the participant will be deemed to not have had tumor progression and may continue treatment with nivolumab after principal investigator review.

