11.1 Definitions

Evaluable for Objective Response Only those patients with measurable disease present at baseline will be enrolled on study.

Only patients who received at least one cycle (6 weeks) of therapy and response assessment with brain MRI or CT at least 6 weeks from the first dose will be considered evaluable for overall survival or disease progression. Patients who discontinue therapy for reasons other than progression prior to response assessment will not be evaluable for survival and will be replaced.

Only patients with measurable disease present at baseline, completing at least one cycle (6 weeks) of therapy, and disease re-evaluated radiographically will be considered evaluable for partial or complete response.

Any patient who initiates treatment and is later found to be ineligible for study (e.g., protocol violation) will be withdrawn from study but will be followed for disease progression, toxicity and survival. The experience of such patients will be characterized separately from that of evaluable patients. Reasons for exclusion of enrolled patients from the analysis set for efficacy, or for safety, will be characterized.

Evaluable Non-Target Disease Response

Patients with lesions present at baseline that are evaluable but do not meet the definitions of measurable disease, have received at least one cycle (6 weeks) of therapy, and have had their disease re-evaluated will be considered evaluable for non-target disease. The response assessment is based on the presence, absence, or unequivocal progression.

All patients who have received at least one dose infusion of nivolumab and/or initiate TTFields therapy are evaluable for safety and toxicity.

Disease Parameters

For the purposes of this study, patients will be evaluated for response approximately every 6 weeks of therapy starting from the first dose for the initial 24 months, thereafter approximately every 8 weeks. In addition to baseline scans, confirmatory scans will be obtained at \geq 4 weeks following initial documentation of objective response or disease progression.

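### Section 5.8 gives two progression triggers for stopping treatment, and the protocol leaves the wait for confirmation, new lesions and Arm A unreconciled

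*Combined protocol and SAP*

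**What the plan says.** Section 5.8, on taking a participant off protocol therapy, opens with "Treatment will be discontinued for clinical or radiographic progression of disease". The list that follows in the same section allows treatment to run until, among other events, "Confirmed radiographic disease progression". The two parts agree on clinical progression, which ends treatment without a repeat scan. They differ only on radiographic progression.

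Elsewhere:

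- Section 1.1 continues infusions to the 24-month maximum or "when there is confirmed tumor progression, intolerable adverse effects or withdrawal of consent". Section 5.1 has the same rule: "when there is confirmed tumor progression, death, intolerable adverse effects or withdrawal".
- Section 5.3 says "Progression should also be confirmed by repeat scans", at least 4 weeks after progression is first suspected. Section 11.1 asks for confirmatory scans at the same interval "following initial documentation of objective response or disease progression".
- Section 11.3.3(a) counts an enhancing-lesion increase above 25% as stable disease unless a later scan confirms it. Section 11.3.3(b) makes a new enhancing measurable lesion progressive disease and states no confirmation.
- The PFS definition in 13.2 asks for radiographic progression to be confirmed at least 4 weeks later.
- Section 5.1 starts ipilimumab "after progression on single agent nivolumab for Arm A"; section 1.1 says the same in substance. Section 5.4 mentions coming off treatment for progression for Arm B only.

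**The concern.** Section 5.8 is where a site looks to decide whether a patient stays on treatment, and its opening sentence is mandatory. Read literally, that sentence ends treatment at one radiographic finding, while the list a few lines below waits for a second. In Arm A the same event is a reason to stop in one section and a reason to add a drug in another.

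The statistical interest is in what the progression call controls. Under 11.5 the best-response window runs from treatment start to disease progression, so the call fixes which scans can supply a response for the primary ORR. The PFS event in 13.2 depends on the same call. If stopping, the ipilimumab trigger and the endpoint definitions use different progression terms, a patient can be off treatment for progression while still counted as stable disease.

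**Working it through.** No figure in the plan states the size of this issue, so the check sets the sections side by side.

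**1. The term each section uses**

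| Section | Use | Confirmation? |
|---|---|---|
| 5.8, opening | stop treatment | not stated |
| 5.8, list | stop treatment | yes |
| 1.1 and 5.1 | end of infusions | yes |
| 5.3 and 11.1 | repeat scan | yes, at 4 weeks or later |
| 11.3.3(a) | size increase above 25% | yes; otherwise stable disease |
| 11.3.3(b) | new enhancing lesion | not stated |
| 13.2 | PFS event | yes, at 4 weeks or later |
| 11.5 | end of best-response window | not stated |
| 1.1 and 5.1 | Arm A ipilimumab trigger | not stated |
| 5.4 | coming off treatment for progression | not stated; Arm B only |

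The weight of the text is towards confirmation.

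**2. A first scan showing growth.** Under 11.3.3(a) an unconfirmed increase is not progressive disease. If the opening of 5.8 is read with that definition, it is not triggered, and the 11.5 window stays open. For this case the conflict is mostly one of wording.

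**3. A first scan showing a new lesion.** Under 11.3.3(b) this is progressive disease at once, so the opening of 5.8 applies. The 5.8 list, 5.3, 11.1 and 13.2 still ask for confirmation of radiographic progression. Here the definition itself does not resolve the conflict.

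**4. Between the two scans.** The interval is at least 4 weeks and nivolumab is given every 2 weeks, so 4 / 2 = 2 scheduled infusions are at issue. Sections 1.1 and 5.1 imply that infusions continue, the opening of 5.8 implies that they do not, and no section says in terms what happens.

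**5. Arm A.** Section 5.8 does not distinguish the arms. Progression in Arm A is thus a stop under 5.8 and the start of ipilimumab under 1.1 and 5.1. Section 5.4 fits the second reading. The trigger does not say whether confirmation is needed.

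**6. Follow-up after stopping.** Section 5.4 gives disease-status follow-up to patients who stop for reasons other than progressive disease. Section 5.9 gives survival follow-up by telephone or record review after documented progression. Sections 5.3 and 11.1 still call for the repeat scan, but neither says that it applies to a patient already off treatment. The end-of-treatment tumour assessment in 5.4 is not timed from the scan that first showed progression, so it need not meet the 4-week interval.

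**7. The progression date.** Section 13.2 does not say whether a confirmed progression is dated at the first or the confirming scan. The two differ by at least 4 weeks.

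**8. Effect on ORR.** This would need the share of patients whose first progression scan would not be confirmed, and the share of those who later respond. The documents give neither, so no effect on ORR or power is calculated.

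**The case against.** The strongest reply is that this is one loose summary sentence in a protocol that otherwise asks for confirmation. Sections 1.1, 5.1, 5.3, 11.1, 11.3.3(a) and 13.2 and the 5.8 list all say so, and for size growth confirmation is part of the definition of progressive disease. The repeat scan is already called for. An investigator who reads the whole protocol would probably not be misled about a patient whose lesion has grown.

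Most of this stands, and it limits the point. It does not answer the new-lesion criterion, the missing statement on infusions between scans, or the Arm A conflict, because the sections cited are silent or disagree on those.

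A reader might infer three stronger things that the documents do not support:

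- **That sites will split and late responses will be lost.** Section 2.4.3 cites a longer time to best response on nivolumab than on bevacizumab (3.0 against 1.5 months), so late response is plausible. It does not say that any response followed a first progression scan. Under 11.3.3(a) a response after unconfirmed growth could still count.
- **That power falls by a stated amount.** Any such figure would rest on invented inputs.
- **That an Arm A response after ipilimumab is wrongly credited, so the window should close at the first ipilimumab dose.** Sections 1.2 and 13.1 define the primary question as TTFields and nivolumab with or without ipilimumab. Closing the window there would change what is estimated; it would not repair 5.8.

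**Conclusion.** Section 5.8 contradicts itself on radiographic progression. The opening sentence is the outlier against the rest of the protocol; that describes the text and is not a view on which rule is clinically right. Three gaps remain after reading everything together: infusions between the first and confirming scan, the new-lesion criterion, and Arm A.

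The identifiable size is an interval of at least 4 weeks, covering about two scheduled nivolumab infusions and the same minimum uncertainty in a PFS date. For scale only, one patient reclassified in a full arm of 30 moves its ORR by 1/30 = 3.3 percentage points. How many patients would be affected, and in which direction, cannot be derived from the documents. The conclusion rests on the text alone and needs no assumption about response rates.

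**What to change.** Reconcile sections 1.1, 5.1, 5.3, 5.4, 5.8 and 11.3.3 so that one stated progression term governs:

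- stopping treatment, stated separately for each arm;
- the Arm A ipilimumab trigger;
- the progression date that closes the best-response window in 11.5 and the one used for PFS in 13.2.

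The text should say what happens to infusions between the first and the confirming scan, and whether the term covers new lesions as well as growth. These are clinical choices for the sponsor.

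Also state that the repeat scan called for in 5.3 and 11.1 is obtained whether or not treatment was stopped, so that progression can be classified in the same way for every patient.

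The cost is a few sentences in an amendment. The sample size does not change, and the scan is already in the protocol.
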